4.3.2 Randomization

Main Trial (ages 50-75)

At baseline, patients will be randomized 1:1 to Arm 1 (usual care) and Arm 2 (mailed FIT outreach), stratified by site (RCCHC, BRH) and insurance status (Medicare, Medicaid, commercial/private, self-pay/uninsured). The

randomization list will be generated by the study biostatistician using a SAS program for stratified (by site and insurance status) randomization.

Sub-study (ages 45-49)

At baseline, patients will be randomized 1:1 to Arm 1 (experimental arm) and Arm 2 (active comparator arm). The randomization sequence will be generated by the study biostatistician using a SAS program.

4.3.3 FIT Kit Packet Contents and Mailing

Main Trial (ages 50-75)

All FIT kit construction and mailing will be done by UNC project staff. For patients in Arm 2 (intervention arm), we will mail an introductory letter alerting patients to expect a free CRC screening test in the mail. Approximately two weeks later, we will mail a FIT Kit, which consists of a(n): 1) cover letter from RCCHC or BRH reminding the patient s/he is due for CRC screening; 2) study information sheet; 3) education sheet about CRC screening; 4) instructions for completing the FIT; 5) one-sample FIT kit; and 6) pre-paid return mailer for the completed FIT kit (this return mailer includes a lab test form with the patient's name, address, date of birth, and medical record number). For pragmatic reasons, FIT kits will be mailed across multiple waves (rather than to all patients at once) over the course of several months. The FIT mailing materials were developed and tested during the pilot phase of this study. They have now been adopted by each clinic as their standard of care for mailed FIT outreach.

The mailing schedule is depicted in the Main Trial Schema (section 4.1). Patients in Arm 2 who do not return the FIT kit within 2-3 weeks, will receive Reminder Letter 1. If they do not return the FIT kit within 2-3 weeks after Reminder Letter 1, they will receive Reminder Letter 2.

Sub-study (ages 45-49)

All FIT kit construction and mailing will be done by UNC project staff.

For patients in both arms, we will follow the same mailing schedule that applies to Arm 2 in the Main Trial. The mailing schedule is depicted in the Sub-study Schema (section 4.1). Arms will differ as follows: Arm 1 (experimental arm): FIT kit is packaged in a padded envelope with a message (e.g., "Important information from your doctor") and a United States Postal Services tracking label, and Type 2 (active comparator arm): FIT is packaged in a plain white envelope without a sticker message or tracking label.

4.3.4 FIT Return and Sample Processing

Main Trial

As described in section 4.3.3, participants in Arm 2 will be provided with a pre-paid return mailer for their completed FIT kit. This pre-paid mailer is addressed to the laboratory. Patients may mail the completed kit directly to the laboratory or can bring it to the FQHC, who will send the sample to the laboratory for processing. The laboratory will relay the test results to the appropriate FQHC. Each FQHC assigns appropriate FQHC staff members to ensure test results of all patients, regardless of study participation, are entered into the EHR per their usual protocols.

Sub-study (ages 45-49)

For all patients in the sub-study (Arms 1 and 2), the FIT return and sample processing procedures will be exactly the same as those described above for Arm 2 participants in the Main Trial.

4.3.5 Notification of Results and Follow-up on Positive FITs

Negative FIT result: BRH patients with a negative FIT result, per BRH current clinical protocol, will receive a letter from their primary care provider. For RCCHC patients with a negative FIT result, IRB-approved UNC research staff will send patients a letter (approved by RCCHC) to notify them of the negative result. The letter will include a reminder that the test should be repeated in 12 months.

Positive FIT result: For patients with a positive (abnormal) FIT result, the patient's primary care provider or the provider's designee will call the patient, per current standard protocol at each FQHC. The primary care provider or primary care provider's designee will inform the patient of the positive result and need for a follow-up colonoscopy. After a patient is notified of a positive result, the patient navigator (employed by UNC and credentialed by each FQHC) will call the patient to offer information and support, including navigation services to access colonoscopy. Navigation services include, but are not necessarily limited to, referral and assistance with registering for charity care programs operating in each region (Hertford Health Access program for RCCHC and Digestive Health Partners-Hendersonville or Pardee Hospital Charity Care program for BRH) including no-cost colonoscopy (for uninsured patients) and, if available, transportation services to and from the colonoscopy appointment (for all patients). Patients who do not qualify for charity care may receive no-cost colonoscopy, supported using study funding and/or donated colonoscopy services. The patient navigator will help navigate the patient to these services, if needed.

4.3.6 Data Collection

REDCap database: RCCHC and BRH will securely transfer patient information from the EHR to a secure SharePoint folder at UNC. A UNC research assistant will then upload the data to a REDCap database (developed based on two previous completed or ongoing studies). Data will include, but not necessarily be limited to, patient name, age, sex, race/ethnicity, mailing address, identified primary care provider, and if possible, the number of visits within the past 18 months with that provider. The study team has fully executed data use agreements in place with each FQHC. Designated approved members of the research team members will use the REDCap database to document whether patients were mailed a FIT kit and to track the status of FIT kit completion (yes or no), test result (positive or negative), contact with patients who have positive results (yes or no), and receipt of navigation support for colonoscopy (yes or no), including referrals for no-cost follow-up colonoscopy (yes or no) and transportation services (yes or no). Approved members of the UNC research team will also document in the REDCap database whether patients call to report they are ineligible for FIT screening per their screening and relevant medical history (e.g., already completed CRC screening elsewhere, have a medical history that places them at higher than average risk for CRC).

EHR: Each CHC will specify, train, and credential members of the UNC research team to conduct a manual review of participant EHRs 6 months or more after randomization to determine whether patients completed any CRC screening test (FIT, colonoscopy, flexible sigmoidoscopy, Cologuard) and, if so, the test result. As mentioned in the preceding paragraph, these data will be entered directly into the REDCap database by IRB-approved UNC staff members for analysis.

Charity Care Program: Hertford Health Access will oversee no-cost follow-up colonoscopy and transportation service to and from medical appointments for RCCHC patients. Digestive Health Partners-Hendersonville and Pardee Hospital Charity Care program provide no-cost colonoscopy services for BRH patients. The patient navigator will contact the local charity care program (Hertford Health Access, Digestive Health Partners, or Pardee Hospital) to acquire data on whether patients from our cohort (who had a positive FIT result) received no-cost follow-up colonoscopy and transportation service. The patient navigator will store these data in the secure REDCap database.

Surveys and interviews (applicable only to participants ages 50-75 in the Main Trial): We will use brief surveys and semi-structured interviews to assess providers' perceptions about the acceptability, appropriateness, and feasibility of the mailed reminder plus FIT kit program. We also will recruit up to 15 patients from each FQHC (RCCHC and BRH) to participate in a 30-45-minute interview to better understand factors that affect their completion of a follow-up colonoscopy following a positive (abnormal) FIT result. Spanish-speaking patient participants will be eligible to participate in the interviews. Patient interviews will be conducted by phone or in person. For provider interviews we will recruit up to 10 FQHC and GI providers associated with each FQHC site. Provider interviews

will be conducted in person or by phone depending on the providers' preference. Interviews will be audio recorded and transcribed verbatim. Personally identifiable information will be redacted from the transcripts prior to analysis. Patients aged 45-49 will not be invited to participate in interviews.

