2.0 STUDY OBJECTIVES AND ENDPOINTS

2.1 Primary Objective (Aim 1)

Main Trial (ages 50-75)

The primary objective of this study is to assess the effectiveness of a mailed FIT outreach program on CRC screening completion in a community health center context in both northeastern and western North Carolina, by comparing the proportion of patients aged 50-75 years screened (as indicated by FIT or colonoscopy completion, assessed in the electronic health records [EHRs]), in the intervention arm and the control arm, 6 months post-intervention. Because both FIT and colonoscopy are viable CRC screening options and some patients may opt for a colonoscopy instead of the FIT, our measure of CRC screening completion includes both FIT and colonoscopy completion. We hypothesize that CRC screening completion rates will be higher among patients in Arm 2, compared to patients who received usual care in Arm 1.

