4.3.7 Number and Duration of Contact with Patients

4.3.7.1 CRC Screening

Patients in the Main Trial control arm (ages 50-75) will not be contacted. Patients in the Main Trial intervention arm (ages 50-75) and patients the Sub-study (ages 45-49) intervention arm and comparator arm will receive an Introductory Letter (first contact) that notifies the patient to expect a FIT kit in the mail. This mailing will allow the study team to identify patients with incorrect addresses before mailing the FIT kit.

After mailing the FIT kit (second contact), the study team will make up to two reminder attempts to follow up with patients in the intervention arm (Arm 2) who have not returned a completed FIT kit. If the FIT kit is undeliverable and returned to the study team because of an incorrect address, the patient will be removed from future Reminder Letter mailings.

Main Trial Patients (ages 50-75) in Arm 2 will receive up to two reminder letters (third and fourth contact). All sub-study patients (ages 45-49) in the intervention and comparator arms also will receive up to two reminder letters (third and fourth contact).

For patients who complete a FIT kit and have a negative result: The patient will be notified of the test result by letter (see section 4.3.5).

For patients who complete a FIT kit and have a positive (abnormal) result: The patients' primary care provider or the primary care provider's designee will notify the patient of the results. After the patient is notified of their positive result, the patient navigator (employed by UNC and credentialed by RCCHC and BRH) will contact the patient by phone or, if phone contact is not successful, by mail to offer information and support for accessing follow-up colonoscopy. Communication will include information about no-cost colonoscopy (for uninsured patients) and transportation service to and from the colonoscopy appointment (for all patients). The patient navigator will call the patient up to three additional times to support the patient in scheduling an appointment for a follow-up colonoscopy, preparing for the colonoscopy procedure, accessing transportation, and financial services, and understanding colonoscopy results. The approximate duration of each phone call will be 5-15 minutes.

The total number of contacts initiated by the study team will range from **3** (Introductory Letter + FIT kit mailing + results letter/call) to **9** (Introductory

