7.4 Data Management/Audit

Study team members will enter data into separate REDCap databases. Study data will be stored securely and managed through the REDCap databases.

As an investigator-initiated study, the trial will also be audited by the Lineberger Cancer Center audit committee every six or twelve months, depending on the participation of affiliate sites.

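### Primary-outcome chart review is not masked, and its results go into the database that reveals the arm; the stated entry route can be improved cheaply

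*Combined protocol and SAP*

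**What the plan says.** All references are to the combined protocol and SAP.

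- **Outcome.** Section 2.1 defines the primary outcome as completion of FIT or colonoscopy, taken from the electronic health record (EHR), at 6 months.
- **Who reads the charts.** Section 4.3.6 (EHR paragraph): "Each CHC will specify, train, and credential members of the UNC research team to conduct a manual review of participant EHRs". The review looks for FIT, colonoscopy, flexible sigmoidoscopy and Cologuard.
- **Where results go.** Same paragraph: "these data will be entered directly into the REDCap database by IRB-approved UNC staff members for analysis". It refers back to the paragraph before it, which describes the REDCap database.
- **What that database holds.** Designated research team members "use the REDCap database to document whether patients were mailed a FIT kit and to track the status of FIT kit completion". They also record the test result, contact after a positive result, and navigation support.
- **Who mails.** Section 4.3.3: "All FIT kit construction and mailing will be done by UNC project staff".
- **Controls.** Section 4.3.7.1: "Patients in the Main Trial control arm (ages 50-75) will not be contacted".
- **Databases.** Section 7.4: "Study team members will enter data into separate REDCap databases". It does not say what separates them.

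Three further statements bear on the risk. Under section 4.3.4, clinic staff enter test results in the EHR for all patients, whether or not they are in the study. Under section 4.1, both arms are tracked over the same period, with controls selected to match each mailing wave. Section 4.3.1 accepts that the EHR may not show screening done at another facility.

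**The concern.** Manual abstraction depends on how hard the reviewer looks and on how borderline records are dated and classified. A reviewer who can see that a kit was mailed, and whether it came back, knows the arm before opening the chart. In Arm 2 a completed-kit entry also says that there is a test to find. No such entry arises from the program for a control. Arm 2 has other sources that controls lack: calls reporting screening done elsewhere, navigator contact, and charity-care colonoscopy data.

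If search effort or dating then differs by arm, the primary comparison carries an ascertainment difference that randomization does not remove and a larger sample does not dilute. The arm could be left off the reviewer's list and entry form, and the plan does not provide for this.

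**Working it through.** **1. Does the entry route reveal the arm?** Reading the sections together:

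- Chart findings go into the REDCap database described in the preceding paragraph of section 4.3.6.
- That database holds mailing and kit-completion status (same section).
- Controls receive no mailing (section 4.3.7.1).
- So a mailing entry means Arm 2, and its absence from a patient's wave points to control.
- Section 7.4 mentions separate databases but does not tie the separation to arm, role or mailing status.
- No section provides for masked, duplicate or independent chart review, or for a common search rule.

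**2. Which tests are exposed?** Arm 2 kits go to the laboratory, which reports to the clinic, and clinic staff enter the result. Usual care is visit-based FIT (section 1.1), and the same entry rule covers all patients. In-house FIT results are therefore fairly safe in both arms. What remains is colonoscopy and other non-FIT tests, and tests dated near the edge of the window. Dating needs particular care: section 4.3.6 times the review at 6 months or more after randomization, section 7.3.1 uses 6 months after FIT mailing, and controls have no mailing date of their own.

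**3. The plan's own figure.** Inputs from section 7.2: 25% v 17%, one-sided alpha 0.0125, power 80%.

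n = [z(0.9875)·√(2·0.21·0.79) + z(0.80)·√(0.17·0.83 + 0.25·0.75)]² / 0.08²

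= [2.2414·0.5760 + 0.8416·0.5732]² / 0.0064 = 491.5, rounded up to 492 per arm per stratum.

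492 × 2 × 4 = 3,936, as stated. Masking the review does not change this number.

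**4. Illustration of size.** The document gives no miss rates, so all of these are assumed. With miss rates m₂ (Arm 2) and m₁ (control), the observed difference is 0.25(1 − m₂) − 0.17(1 − m₁).

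| Assumed misses, Arm 2 / control | Calculation | Observed difference |
|---|---|---|
| none / none | 0.25 − 0.17 | 8.0 points |
| 2% / 5% | 0.2450 − 0.1615 | 8.35 points |
| 2% / 10% | 0.2450 − 0.1530 | 9.2 points |
| 5% / 2% (reversed) | 0.2375 − 0.1666 | 7.09 points |
| 10% / 2% (reversed) | 0.2250 − 0.1666 | 5.84 points |

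The inflation in the second and third rows is 0.35 to 1.2 points. These rows apply the rates to every completed test. If only half of the completed tests in each arm were exposed, it would halve to about 0.18 to 0.6 points.

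**5. Illustration with no true effect.** Take 17% in both arms, 2% missed in Arm 2 and 5 to 10% in controls. The observed rates are 16.66% v 16.15% to 15.30%, a false difference of 0.51 to 1.36 points. By the normal approximation to the two-proportion test:

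- Stratum test (492 per arm, one-sided 0.0125): false-positive probability 0.021 to 0.049.
- Overall test (2,000 per arm; one-sided 0.05 is assumed, because no alpha is stated for it): 0.11 to 0.32.

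These again apply the miss rates to all tests. They show that a small difference in ascertainment matters more for the large overall test than for a stratum test. They do not estimate what will happen.

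**6. Could this produce the whole planned effect?** With a true rate of 25% in both arms and no misses in Arm 2, 0.08/0.25 = 32% of control screenings would have to be missed.

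**The case against.** The case for leaving the plan alone has four parts.

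- **Same team is not same people.** Kits are mailed by UNC project staff, tracked by designated team members, and charts are read by members whom each center credentials. A reader might infer that the people who mail kits also judge the outcome. The document does not say so. Nor does it say which fields a reviewer sees on screen. This stands: the gap is that masking is not provided for, not that unmasked review by the mailing staff is prescribed.
- **The outcome is largely objective.** Most completions are likely to be FITs, and their results are entered by clinic staff in both arms over the same tracking period. Searching harder cannot find a test that is not in the chart. This stands, and it narrows the risk to non-FIT tests and borderline dates.
- **The direction is not fixed.** A reader might infer a bias toward the intervention. The plan expects 25% of Arm 2 to be screened, so most Arm 2 entries would show no completed kit, and a reviewer might search those charts less hard for a colonoscopy. That would bias toward no difference. This stands.
- **The arm cannot be fully hidden.** Some charts will show a mailed kit or navigator contact. This also stands, but partial masking is still better than an entry screen that discloses the arm for every patient.

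None of these points supplies a masked review or a common search rule.

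**Conclusion.** The concern holds in limited form. The primary outcome is abstracted by research team members and entered where mailing status discloses the arm, and the plan has no safeguard against that knowledge affecting the search. This rests on reading the EHR paragraph of section 4.3.6 as pointing to the kit-tracking database, which its own cross-reference supports and section 7.4 does not contradict.

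The exposure is mainly to colonoscopy, other non-FIT tests and borderline dates. Neither size nor direction can be derived from the document. The inflation of about 0.4 to 1.2 points depends entirely on assumed miss rates, and the opposite assumption gives attenuation. The stronger reading, that the planned effect could be an artefact of unmasked review, is not supported: it would take about 32% of control screenings missed with none missed in Arm 2. This is a worthwhile low-cost improvement to the ascertainment method, not a demonstrated flaw in the result.

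**What to change.** Amend section 4.3.6 as follows:

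1. Give reviewers a worklist with the patient identifier needed to open the chart and a wave index date, but no arm. Section 4.1 already matches controls to mailing waves, so an index date can be assigned in both arms.
2. Have them record outcomes on a separate REDCap form with the mailing, kit-tracking and navigation fields hidden.
3. Apply one written search checklist and one date window, counted from the index date, to every chart in both arms. Reconcile the timing wording in sections 4.1, 4.3.6 and 7.3.1 with that window.
4. State that the primary outcome uses only this review. Kit tracking, patient calls and navigator or charity-care data would serve the other aims.
5. Lock the outcome form before merging it with the allocation.

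The cost is setting up one form, one worklist and one checklist. The credentialed staff already planned can do the work, and the sample size is unchanged. The drawback is that masking is partial, because some charts will still reveal the mailed kit or navigator contact; the common checklist and window protect those charts too.

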2.2 Secondary Objectives

Main Trial (ages 50-75)

Other objectives of this study are to assess implementation determinants and outcomes to inform plans for sustaining and scaling the CRC screening program. Our aims are to:

Aim 2: Assess the logistical feasibility and patient and provider acceptability of the mailed FIT outreach program (Arm 2), and

Aim 3: Estimate the cost and cost-effectiveness per person screened in each arm, as well as the level of resource investment required to scale-up the program statewide.

Sub-study (ages 45-49)

A new, secondary objective of this trial is to assess screening completion of a mailed FIT outreach program in patients aged 45-49 who are patients at the clinic.

We will:

1. Compare the proportion of patients who are current with any CRC screening prior to mailed FIT outreach and within 60 days of FIT mailing per electronic health record (EHR) query
2. Compare the proportion of patients who complete FIT within 60 days of the mailed FIT date, by experimental and active comparator arms
3. Describe the demographic characteristics of patients who complete FIT including, but not limited to, patient race, ethnicity, sex, and insurance status.

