3.0 PATIENT ELIGIBILITY

We will use the inclusion and exclusion criteria below to guide our electronic health record (EHR) query to identify eligible patients for the main trial and added cohort of patients ages 45-49.

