3.1 Inclusion Criteria

Individuals must meet all of the following inclusion criteria to participate in this study:

- 3.1.1 Main trial: Age 50-75 years; Sub-study: Age 45-49 years
- 3.1.2 At average risk for CRC (“average risk” is defined as those patients who do not have any of the following: history of CRC, colonic adenomas, family history of CRC, or diagnosis of inflammatory bowel disease)
- 3.1.3 No record of fecal occult blood test (FOBT)/FIT within the past 12 months or colonoscopy within 10 years, sigmoidoscopy within 5 years, barium enema within 5 years, or computed tomography (CT) colonography within 10 years of the EHR query date
- 3.1.4 No record of any CRC diagnosis or total colectomy
- 3.1.5 Active patient (seen within the past 18 months) of RCCHC or BRH

Patients invited to participate in an interview will meet three additional inclusion criteria: aged 50-75; be assigned to study Arm 2 in the Main Trial; and have a positive (abnormal) FIT result as a participant in the screening program. We will not interview participants who are aged 45-49.

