3.2 Exclusion Criteria

[figure not shown]
All individuals meeting any of the exclusion criteria at baseline will be excluded from study participation:

- 3.2.1** Main trial: Age younger than 50 years or older than 75 years; Sub-study: Age younger than 45 years or older than 49 years
- 3.2.2** Not at average risk for CRC (“average risk” is defined as those patients who do not have any of the following: history of CRC, colonic adenomas, family history of CRC, or diagnosis of inflammatory bowel disease)
- 3.2.3** Record of FOBT/FIT within the past 12 months or colonoscopy within 10 years, sigmoidoscopy within 5 years; barium enema within 5 years, or CT colonography within 10 years of the EHR query date
- 3.2.4** Record of any CRC diagnosis or total colectomy
- 3.2.5** Not an active patient (not seen within the past 18 months) of RCCHC or BRH

Patients will not be invited to participate in an interview if they meet additional exclusion criteria: be assigned to study Arm 1, do not return a FIT as a participant in the screening program, or have a negative (normal) FIT result as a participant in the screening program.

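### The baseline look-back omits Cologuard but the follow-up chart review records it, so patients already screened by it enrol as due and could inflate the sub-study's before-after change

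*Combined protocol and SAP*

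**What the plan says.** **Who is due.** Section 3.0 ties the criteria to the record search in the main trial and the 45-49 cohort alike: "We will use the inclusion and exclusion criteria below to guide our electronic health record (EHR) query". Criterion 3.1.3 requires "No record of fecal occult blood test (FOBT)/FIT within the past 12 months or colonoscopy within 10 years, sigmoidoscopy within 5 years", and the list ends with "barium enema within 5 years, or computed tomography (CT) colonography within 10 years of the EHR query date". Exclusion 3.2.3 mirrors it, starting "Record of FOBT/FIT within the past 12 months or colonoscopy within 10 years, sigmoidoscopy within 5 years". Neither list contains Cologuard. Section 4.1 applies the same screening-history criterion again before round 2.

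**What is recorded afterwards.** Section 4.3.6 describes a manual EHR review, 6 months or more after randomization, to establish whether patients completed any CRC screening test. The tests named are "FIT, colonoscopy, flexible sigmoidoscopy, Cologuard". Cologuard is named separately from FIT.

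**Which outcomes use which tests.** The main-trial primary outcome (2.1) is FIT or colonoscopy. Sub-study Outcome 2 (2.2, 7.1) is FIT return by envelope type. Sub-study Outcome 1 (2.2) is broader: "Compare the proportion of patients who are current with any CRC screening prior to mailed FIT outreach and within 60 days of FIT mailing". It is assessed by EHR query, and 7.2 frames the test as one of conversion from not screened to screened.

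**The concern.** A before-after comparison in one cohort is sound only if the same definition of screened applies at both times. Here the only list that sorts patients into current and due leaves out a test that the only follow-up list includes. A patient with a Cologuard result before mailing is classed as not current at baseline. If that result is accepted at follow-up, the patient becomes a conversion without having done anything in response to the outreach. There is no control group in which the same reclassification would cancel out.

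Two things are at stake. The first does not depend on how Outcome 1 is scored: under the query as written, patients whom 4.3.6 would recognise as screened are enrolled and, in the mailed arms, sent kits as if due. The same holds at round 2, where a Cologuard recorded in the round 1 review would not make the patient ineligible under 3.1.3. The second is possible upward bias in the reported change in screening at ages 45-49.

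**Working it through.** **Step 1. Compare the lists.**

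| Test | Look-back (3.1.3, 3.2.3) | Follow-up review (4.3.6) |
|---|---|---|
| FIT (look-back: FOBT/FIT) | yes | yes |
| Colonoscopy | yes | yes |
| Sigmoidoscopy | yes | yes |
| Barium enema | yes | no |
| CT colonography | yes | no |
| Cologuard | no | yes |

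The lists differ in both directions. Only the Cologuard row can turn an old test into an apparent new screen.

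**Step 2. Reproduce the plan's figure for Outcome 1.** Section 7.2 gives N = 500, odds ratio 2.922, discordant proportion 0.07, two-sided McNemar test at 0.05 and 80% power. (Section 7.3.4 names a Mantel-Haenszel test for this outcome; I use the test that was powered.)

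- P10 = 0.07 × 2.922 / 3.922 = 0.05215
- P01 = 0.07 / 3.922 = 0.01785
- Exact McNemar power, summed over a Binomial(500, 0.07) number of discordant pairs, is 0.800. The stated 80% reproduces.

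The plan's rounded inputs correspond to 0.052 × 500 = 26 conversions and 0.018 × 500 = 9 reversions. The plan says P01 is assumed and cannot be observed. Against 9 reversions, 21 conversions are needed for significance with the exact test.

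**Step 3. Possible false conversions.** The share s of the 450 mailed patients with an earlier, unlisted Cologuard is not in the documents. I assume 1% to 3%, and that every such result is accepted at follow-up.

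- s = 1%: 0.01 × 450 = 4.5 patients
- s = 2%: 0.02 × 450 = 9 patients
- s = 3%: 0.03 × 450 = 13.5 patients

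That is about 5 to 14 patients: 1 to 3 percentage points of the 450, or 0.9 to 2.7 points of the full 500. Some would also return a FIT and convert genuinely. At 20% return, the false conversions fall to 0.8 × 4.5 = 3.6 and 0.8 × 13.5 = 10.8, or 0.8 to 2.4 points of the 450. So 1 to 3 points is an upper figure for this range of s.

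**Step 4. Set against the expected response.** Section 7.2 assumes a FIT mail-back rate of 0.20 in the plain-envelope arm. Applied to all 450, that is 0.20 × 450 = 90 genuine conversions, well above the 21 needed. Against 9 reversions the McNemar statistic is (90 − 9)² / (90 + 9) = 6561 / 99 = 66.3, compared with a critical value of 3.84. The test result would not rest on 5 to 14 extra patients. The estimated change would still be too large, by 4.5/90 = 5% to 13.5/90 = 15% of the genuine count before allowing for overlap.

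**The case against.** **The link to Outcome 1 is inferred.** The Cologuard list belongs to a manual review at 6 months or more, whereas Outcome 1 is assessed by an EHR query at 60 days. Section 2.2 uses one phrase for both time points, so no change of definition is stated. If the 60-day query reuses the baseline list, no false conversion arises. This stands, and it is why the bias is stated as possible only. It does not remove the point: 4.3.6 is not restricted to the main trial, and the plan gives no other follow-up test list for Outcome 1.

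**Reviewers would count only new tests.** Probably so. For the main trial, 4.1 sets a tracking period that starts at the Introductory Letter. The sub-study has no matching sentence, and being current is a status that an old test can satisfy.

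**Patients can phone in as ineligible** (4.3.1), and screening completed elsewhere is recorded (4.3.6). This is a partial safeguard. It relies on the patient calling, and no rule says how such patients are then analysed.

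**Stronger readings that the documents do not support.**

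- A reader might infer that a handful of false conversions would make Outcome 1 significant: six with no reverse changes gives an exact two-sided p of 2 × 0.5⁶ = 0.031. That holds only if reversions are zero. Six genuine FIT returns would then do the same, so it reflects the unobservable P01, not Cologuard. With the plan's 9 assumed reversions, six conversions are far short of 21.
- A reader might infer that the definition alone could create the whole result. If there were no true net change (P10 = P01 = 0.018), the exact test's rejection rate would rise from 0.029 to 0.109 at s = 1% and 0.616 at s = 3%. But that supposes almost no response to the mailing, contrary to the plan's 20% FIT return.
- A reader might infer that the randomised results are biased. Patients with an earlier Cologuard should fall equally into both arms, and neither the main-trial primary outcome nor Outcome 2 counts Cologuard as defined.

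**Conclusion.** The mismatch is in the current text. Under the eligibility query as written, patients already screened by Cologuard enter both cohorts as due. That much needs no assumption beyond such patients existing.

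The effect on Outcome 1 is conditional. It requires that the 4.3.6 list is used for the 60-day assessment and that a test dated before the outreach is accepted; the plan neither states nor rules out either. If both hold, and 1% to 3% of the 450 have an earlier Cologuard (my assumption), about 5 to 14 false conversions would inflate the change by up to about 1 to 3 percentage points. The bias is in the estimate. At the plan's own assumed FIT return the significance result is unlikely to depend on it. No stated sample size or power figure is affected.

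**What to change.** Reconcile 3.1.3, 3.2.3 and 4.3.6 to one list of tests that includes Cologuard, with its look-back interval set by the study's clinical lead. Use that list at the baseline query, the round-2 re-query and the outcome assessment, and decide at the same time how barium enema and CT colonography are handled at follow-up.

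For Outcome 1, state in 2.2 and 7.3.4 which list applies at 60 days, and that only tests dated on or after the start of outreach count as newly screened. If the query has already been run, the date rule alone removes the false conversions; patients found to have an earlier Cologuard can be reported as a count.

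Cost: one added code set in the EHR query, short edits to these sections, and a few patients leaving the eligible list.
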